8.3. Adverse Events (AEs), Serious Adverse Events (SAEs) and Other Safety Reporting

The definitions of adverse events (AEs) or serious adverse events (SAEs) can be found in Section 10.3.

AEs will be reported by the participant (or, when appropriate, by a caregiver, surrogate, or the participant's legally authorized representative).

The investigator and any qualified designees are responsible for detecting, documenting, and recording events that meet the definition of an AE or SAE and remain responsible for

following up AEs that are serious, considered related to the study intervention or the study, or that caused the participant to discontinue the study intervention or study (see Section 7).

The method of recording, evaluating, and assessing causality of AEs and SAEs and the procedures for completing and transmitting SAE reports are provided in Section 10.3.

8.3.1. Time Period and Frequency for Collecting AE and SAE Information

- All SAEs will be collected from the start of study intervention until the follow-up visit at the timepoints specified in the SoA (Section 1.3). However, any SAEs assessed as related to study participation (e.g., study intervention, protocol-mandated procedures, invasive tests, or change in existing therapy) or related to a GSK product will be recorded from the time a participant consents to participate in the study.
- All AEs will be collected from the start of intervention until the follow-up visit at the timepoints specified in the SoA (Section 1.3).
- Medical occurrences that begin before the start of study intervention but after obtaining informed consent will be recorded as medical history/current medical conditions not as AEs.
- All SAEs will be recorded and reported to the sponsor or designee immediately and under no circumstance should this exceed 24 hours, as indicated in Section 10.3. The investigator will submit any updated SAE data to the sponsor within 24 hours of it being available.
- Investigators are not obligated to actively seek information on AEs or SAEs after conclusion of the study participation. However, if the investigator learns of any SAE, including a death, at any time after a participant has been discharged from the study, and he/she considers the event to be reasonably related to the study intervention or study participation, the investigator must promptly notify the sponsor.

8.3.2. Method of Detecting AEs and SAEs

- The method of recording, evaluating, and assessing causality of AEs and SAEs and the procedures for completing and transmitting SAE reports are provided in Section 10.3.
- Care will be taken not to introduce bias when detecting AEs and/or SAEs. Open-ended and nonleading verbal questioning of the participant is the preferred method to inquire about AE occurrence.

8.3.3. Follow-up of AEs and SAEs

After the initial AE/SAE report, the investigator is required to proactively follow each participant at subsequent visits/contacts. All SAEs, and non-serious AEs of special interest (as defined in Section 8.3.7), will be followed until the event is resolved, stabilized, otherwise explained, or the participant is lost to follow-up (as defined in Section 7.3). Further information on follow-up procedures is given in Section 10.3.

8.3.4. Regulatory Reporting Requirements for SAEs

- Prompt notification by the investigator to the sponsor of an SAE is essential so that legal obligations and ethical responsibilities towards the safety of participants and the safety of a study intervention under clinical investigation are met.
- The sponsor has a legal responsibility to notify both the local regulatory authority and other regulatory agencies about the safety of a study intervention under clinical investigation. The sponsor will comply with country-specific regulatory requirements relating to safety reporting to the regulatory authority, Institutional Review Boards (IRBs)/Independent Ethics Committees (IECs), and investigators.
- An investigator who receives an investigator safety report describing an SAE or other specific safety information (e.g., summary or listing of SAEs) from the sponsor will review and then file it along with the IB and will notify the IRB/IEC, if appropriate according to local requirements.

Investigator safety reports must be prepared for suspected unexpected serious adverse reactions (SUSARs) according to local regulatory requirements and sponsor policy and forwarded to investigators as necessary.

8.3.5. Pregnancy

- Details of all pregnancies in female participants will be collected after the start of study intervention and until the follow-up visit.
- If a pregnancy is reported, the investigator will record pregnancy information on the appropriate form and submit it to GSK within 24 hours of learning of the female participant pregnancy. While pregnancy itself is not considered to be an AE or SAE, any pregnancy complication or elective termination of a pregnancy for medical reasons will be reported as an AE or SAE.
- Abnormal pregnancy outcomes (e.g., spontaneous abortion, fetal death, stillbirth, congenital anomalies, ectopic pregnancy) are considered SAEs and will be reported as such.
- The participant will be followed to determine the outcome of the pregnancy. The investigator will collect follow-up information on the participant and the neonate and the information will be forwarded to the sponsor.
- Any post-study pregnancy-related SAE considered reasonably related to the study intervention by the investigator will be reported to the sponsor as described in Section 8.3.4. While the investigator is not obligated to actively seek this information in former study participants, he or she may learn of an SAE through spontaneous reporting.
- Any female participant who becomes pregnant while participating in the study will discontinue study intervention.

8.3.6. Cardiovascular and Death Events

For any cardiovascular events detailed in Section 10.3 and all deaths, whether or not they are considered SAEs, specific Cardiovascular (CV) and Death sections of the CRF will be required to be completed. These sections include questions regarding cardiovascular (including sudden cardiac death) and non-cardiovascular death.

The CV CRFs are presented as queries in response to reporting of certain CV MedDRA terms. The CV information should be recorded in the specific cardiovascular section of the CRF within one week of receipt of a CV Event data query prompting its completion.

The Death CRF is provided immediately after the occurrence or outcome of death is reported. Initial and follow-up reports regarding death must be completed within one week of when the death is reported.

8.3.7. Adverse Events of Special Interest

Predefined AEs of special interest for this study are CV events, gastrointestinal events, *C. difficile* infection or colitis events, and AEs related to acetylcholinesterase inhibition (see Section 2.3.1), which will be identified by a prespecified list of coded terms or determined by algorithm, as described in the Statistical Analysis Plan (SAP).

8.4. Pharmacokinetics

Whole blood, spot urine and pooled urine samples (approximately blood 3 mL and urine 1mL, respectively) will be collected for measurement of plasma and urine concentrations of gepotidacin as specified in the SoA (Section 1.3).

- Instructions for the collection and handling of biological samples will be provided by the sponsor. The actual date and time (24-hour clock time) of each sample collected will be recorded.
Note: For the pooled urine sample, the volume of complete urination also will be recorded.
- Complete urination is required when collecting a urine sample for bacteriological testing. The time of urination performed is set as the start of the urine pooling and will be recorded.
- At the On-therapy Visit, as the spot urine sample collection coincides with the urine bacteriology sample collection, a single urine sample of adequate volume may be collected and split into separate samples for urine PK and microbiological purposes.
- The date and time of the last dose taken before the PK sample (plasma and urine) collection will be recorded.
Note: The date and time of the last dose taken at home before hospital visit is also needed for the baseline PK sample collection.
- Samples will be used to evaluate the PK of gepotidacin. Each whole blood sample will be processed into plasma.

- PK Samples will be analysed using an appropriately validated assay method by or under the supervision of the sponsor.
- Intervention concentration information that would unblind the study will not be reported to investigative sites or blinded personnel until the study has been unblinded.

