PK blood sample		X	X				
Sparse PK blood samples will be collected.
 
 At the Baseline Visit, the PK blood samples will be collected at 1-2 hours post-dose as peak concentration. At the On-therapy Visit, the PK blood samples will be collected at pre-dose as trough concentration (i.e., 12 hours post-dose, which is at the end of the dosing interval from the previous dose) and at 1-2 hours post-dose as peak concentration. 
(Further detailed information will be provided in the SRM.)

PK urine sample		X	X				
 At the Baseline Visit, samples will be collected from pre-dose to approximately 2 hours (1 to 3 hours) post-dose as pooled urine. At the On-therapy Visit, samples will be collected at pre-dose (i.e., 12 hours postdose as spot urine, which is at the end of the dosing interval from the previous dose) and from pre-dose to approximately 2 hours (1 to 3 hours) post-dose as pooled urine. 
(Further detailed information will be provided in the SRM.)

Study treatment							
Administer oral dose of study treatment		X	X				
 Participants will receive oral study treatment BID for 5 days under double-blind, double-dummy conditions. The first oral dose will be administered at the study site during the Baseline Visit; participants will self-administer as outpatients thereafter, beginning with the second dose, excluding the day of On-therapy Visit (i.e., taking morning dose at study site). Each dose should

Visit	Baseline		On-Therapy ^a	TOC ^b	Follow-up	Early Withdrawal	Notes
Study Day	1		2 to 4	10 to 13	28±3	NA	
be taken after food consumption and with water. The date and time of each dose administered at the study site will be recorded in the source documents.
 
 At the On-therapy Visit, whenever it is possible, the participant will have the pregnancy test performed at the study site. If the visit coincides with the 8th dose, the participant will take their next dose of study treatment at the study site after negative pregnancy test results are confirmed. Note: The On-therapy Visit should be scheduled to support completion of the postdose ECG within the protocol-defined window. Also, in a woman of childbearing potential, the high sensitivity pregnancy test must be performed and show negative results at the latest before Dose 8 of study treatment is taken.
Procedure	Pre-dose	Post-dose					

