8. STUDY ASSESSMENTS AND PROCEDURES

- Study procedures and their timing are summarized in the SoA (Section [1.3](#)).
- Protocol waivers or exemptions are not allowed
- Immediate safety concerns should be discussed with the sponsor immediately upon occurrence or awareness to determine if the participant should continue or discontinue study intervention.
- Adherence to the study design requirements, including those specified in the SoA, is essential and required for study conduct.
- All screening evaluations must be completed and reviewed to confirm that potential participants meet all eligibility criteria. The investigator will maintain a screening log to record details of all participants screened and to confirm eligibility or record reasons for screening failure, as applicable.
- Procedures conducted as part of the participant's routine clinical management (e.g., blood count) and obtained before signing of ICF may be utilized for screening or baseline purposes provided the procedure met the protocol-specified criteria and was performed within the timeframe defined in the SoA.
- Prescreening activities may be conducted, including a prescreening informed consent and urine testing, as further detailed in the SRM. The required baseline urine

specimen may be collected as part of an optional prescreening process, if not already part of standard of care, and is further detailed in the SRM. This specimen can be used for the required baseline procedures of the diagnosis of presumptive acute uncomplicated cystitis and pregnancy testing.

- Laboratory results that could unblind the study will not be reported to investigative sites or other blinded personnel until the study has been unblinded.
- The maximum amount of blood collected from each participant over the duration of the study, including any extra assessments that may be required, will not exceed 200 mL.
- Repeat or unscheduled samples may be taken for safety reasons or for technical issues with the samples.
- Participants may return to the study site at any time due to AEs or if they are experiencing new or continuing signs and symptoms of acute cystitis. Participants will be assessed and treated per the investigator's judgement. If a participant is switched to a different antimicrobial before or during the TOC Visit, all TOC procedures should be completed before the other antimicrobial is started.

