- Each treatment day will be assessed over 24 hours starting with the first dose of study treatment, as further detailed in the SRM.

The study will comprise the following 4 planned study visits:

Note: For all study visits, to minimize the amount of time that participants spend at the clinic, eConsent may be utilized and remote collection of study-related data may be obtained as described in the SRM. Thus, some visit data may be collected through a combination of telemedicine and on-site visits. Collection of information via telemedicine will be performed only where local regulations permit.

- **Baseline (Day 1) Visit:** The Baseline Visit will be performed before dosing on Day 1. Assessments will be performed as shown in the SoA (Section 1.3), including the following:
 - Pretreatment baseline specimens for microbiological testing will be collected, as described in Section 8.1.2 Clinical signs and symptoms of acute cystitis will be recorded, as described in Section 8.1.3.1 and 10.10. CCI [REDACTED]
[REDACTED].
 - Following completion of all pretreatment assessments, eligible participants will be randomly assigned to a study treatment, as described in Section 6.3.
 - The first dose of randomly assigned oral study treatment will be administered at the study site. Participants will remain at the study site approximately 2 hours (1.5 to 4 hours) after dosing, during which time all Day 1 posttreatment assessments will be performed (i.e., triplicate ECG and postdose plasma and pooled urine PK sample collection), as shown in Section 1.3. Any AEs or clinically significant changes should be followed accordingly. Subsequent to administration of the first dose at the study site, participants will self-administer doses as outpatients thereafter, beginning with the second dose, excluding the

day of On-therapy Visit. (Note: Each dose should be taken after food consumption and with water.)

- The On-therapy, TOC, and Follow-up Visits should be scheduled before the participant leaves the study site on Day 1 (as per the Schedule of Activities Table in Section 1.3); the planned return day/time should be at the convenience of the participant and also the availability of the study site staff.

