#### 4.3.8.2. Main analytical approach

The analysis is based on the PK population.

All calculations of PK concentrations will be based on actual sampling times that fall within the set PK windows described below.

Summary statistics (n, arithmetic mean, geometric mean, median, standard deviation, minimum, maximum, 95% CI of the arithmetic and geometric means and between participant coefficient of variation [%CV and %CVb]) for plasma and urine gepotidacim concentrations will be provided by the sampling windows in [Table 1](#). If PK concentrations are not quantifiable, these values will be imputed as 0.

PK samples collected outside of the treatment phase will only be listed.

If more than one concentration data is available within the same PK window at a scheduled time point, the data closer to 12 hours post-latest dose will only be used for the summary statistics of Pre-Dose. For Post-Dose, data closer to 2 hours post-latest dose will only be used for the summary statistics.

[figure not shown]
PK concentrations will be listed based on PK (Full) population (i.e. including the participants impacted by GCP violation).

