**Table 1 PK Summary by sampling windows**

Visit	Parameter	PK Window
Baseline Study Day 1	$C_{day1, 0-2h}$	Average concentration post-dose 0 to $\leq 2$ hours
	$C_{day1, >2h}$	Average concentration post-dose $>2$ hours
	$C_{day2-5, pre-dose}$	Average concentration pre-dose
On-Therapy Study Day 2 to 5	$C_{day2-5, 0-2h}$	Average concentration post-dose 0 to $\leq 2$ hours
	$C_{day2-5, >2h}$	Average concentration post-dose $>2$ hours

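### The Day 1 urine pool opens before the dose, so drug-free urine lowers a gepotidacin concentration that the SAP labels as post-dose

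*Protocol*

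**What the plan says.** Protocol Section 8.4 requires complete emptying of the bladder for the bacteriology sample and ties the pool to that moment: "The time of urination performed is set as the start of the urine pooling and will be recorded". It also has the pooled volume and the sampling and dosing times recorded. The Schedule of Activities (Section 1.3) gives the Day 1 interval: "At the Baseline Visit, samples will be collected from pre-dose to approximately 2 hours (1 to 3 hours) post-dose as pooled urine".

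Protocol Section 8 fixes the order on Day 1. "Pretreatment baseline specimens for microbiological testing will be collected" is a step of the Baseline Visit before dosing. Then: "Following completion of all pretreatment assessments, eligible participants will be randomly assigned to a study treatment". The first dose comes after that.

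SAP Section 4.3.8.2 summarises plasma and urine concentrations by the windows of Table 1 ("PK Summary by sampling windows"). For Day 1 the table has two rows, one for up to 2 h after the dose and one for more than 2 h after it. The visible SAP text uses neither the pooled volume nor the pool start time.

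**The concern.** Previous treatment with gepotidacin is an exclusion criterion (Protocol Section 5.2), so urine formed between the bacteriology void and the first dose contains no drug. It enters the pool and can only dilute it. No visible passage limits that gap or asks for a second void at dosing. The reported Day 1 value therefore mixes drug excretion with the length of the wait before dosing, which will differ between participants.

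The SAP adds two problems of its own. The row labels describe a post-dose concentration, but the pool opens before the dose. In addition, the cut at 2 h suits plasma, which is drawn 1 to 2 h after the dose, but it falls on the nominal urine collection time. Participants who all comply with the 1 to 3 h urine window will be divided between two rows by small differences in timing.

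Gepotidacin urine concentration is a named secondary endpoint. A downward shift on Day 1 that comes from procedure could be read as lower urinary exposure in Japanese participants.

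**Working it through.** The documents state no void-to-dose interval, dilution factor or expected pooled concentration, so there is no planned figure to reproduce. The check is a mass balance.

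**Inputs**
- T_post, time from dose to end of pool: 1, 2 or 3 h (Schedule of Activities).
- Drug in urine formed before the Day 1 dose: none (exclusion of earlier gepotidacin treatment).
- T_pre, time from bacteriology void to dose: not given. Assumed range 0.25 to 3 h.
- f, urine flow before the dose relative to flow after it: not given. Assumed 1, then varied from 0.5 to 2.

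**Formula**

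All the drug in the pool is excreted after the dose, while the volume covers both intervals. Hence

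pooled concentration / undiluted post-dose concentration = T_post / (T_post + f × T_pre).

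For example, with T_post = 2, T_pre = 1 and f = 1, the ratio is 2 / (2 + 1) = 0.67.

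**Results with f = 1**

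| T_pre (assumed) | T_post = 1 h | T_post = 2 h | T_post = 3 h |
|---|---|---|---|
| 0.25 h | 0.80 | 0.89 | 0.92 |
| 0.5 h | 0.67 | 0.80 | 0.86 |
| 1 h | 0.50 | 0.67 | 0.75 |
| 2 h | 0.33 | 0.50 | 0.60 |
| 3 h | 0.25 | 0.40 | 0.50 |

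**Sensitivity to flow.** At T_pre = 1 h and T_post = 2 h, the ratio is 2 / 2.5 = 0.80 if flow before the dose is half the later flow, and 2 / 4 = 0.50 if it is double.

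**Does the amount excreted escape the problem?** Take an illustrative 100 mg excreted by 2 h and a flow of 100 mL/h:

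| T_pre | Volume | Concentration | Concentration × volume |
|---|---|---|---|
| 0 h | 200 mL | 500 µg/mL | 100 mg |
| 0.5 h | 250 mL | 400 µg/mL | 100 mg |
| 1 h | 300 mL | 333 µg/mL | 100 mg |
| 2 h | 400 mL | 250 µg/mL | 100 mg |

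The concentration halves across the table while the amount does not move. On Day 1 the recorded volume is therefore enough to remove the dilution, provided the whole pool is measured.

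**The 2 h cut.** The permitted urine collection runs from 1 to 3 h, centred on about 2 h. A pool closed at 1 h 55 min goes in the first row and one closed at 2 h 05 min in the second, although both comply. The SAP rule that "data closer to 2 hours post-latest dose will only be used for the summary statistics" chooses between several values in one window for one participant. It does not bring these two participants together.

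**The case against.** The pre-dose start is stated openly in the Schedule of Activities, so it is a disclosed choice. The gap may be short: at 0.25 h with a 2 h collection the loss is about 11%. The urine PK row defers further detail to the Study Reference Manual, which may require a void at dosing or limit the gap. The exploratory parts of the SAP are redacted and might use the volume. Dosing need not wait for most laboratory results either: study tests other than dipstick and pregnancy tests go to a central laboratory (Protocol Section 10.2), and Section 7.1.3 provides for low baseline creatinine clearance in participants already on treatment. All of this stands and leaves the size open. It does not change the direction for any gap above zero, nor the mismatch between the row labels and the collection interval.

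Several stronger readings are tempting but not supported:
- *The void precedes eligibility testing, or is the nitrite/pyuria specimen.* These are separate rows in the Schedule of Activities, and no passage links them.
- *The pool could open at prescreening.* Protocol Section 8 says a "specimen may be collected as part of an optional prescreening process", but the uses it names are diagnosis and pregnancy testing, not bacteriology. SAP Section 4.1.2 does accept urine from the day before dosing, but as the microbiological baseline, not as a pool start.
- *The bias follows site workflow.* Nothing describes site workflow. Variation between participants is as far as the text goes.
- *The change from Day 1 to the On-therapy Visit is biased upward.* The visible SAP plans no such comparison; it summarises each window on its own.
- *The dose rationale is undermined.* Protocol Section 4.3 rests on earlier studies and modelling, not on this sample.

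**Conclusion.** The point holds in limited form. Followed as written, the plan pools drug-free urine with post-dose urine on Day 1 and reports the result under a post-dose label, in rows cut at the nominal collection time. The labelling and the cut need no assumption. The dilution has a certain direction for any gap above zero but an unknown size, and every ratio above rests on an assumed gap and flow. The effect is confined to the descriptive urine PK summary. The primary endpoint is untouched, and so is the population PK model, which uses plasma concentrations (Protocol Section 9.3.5). The change is worth making because the endpoint is a named one and the data needed to correct it are already recorded.

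**What to change.** In SAP Section 4.3.8.2 and Table 1:
- Summarise pooled urine separately from plasma, in one window labelled as running from before the dose to 1 to 3 h after it.
- Beside concentration, report amount excreted (concentration × recorded pooled volume).
- Show the void-to-dose and dose-to-collection intervals. Amount excreted still depends on when in the 1 to 3 h window the pool was closed, so it should not be shown without them.
- Note that the correction applies to Day 1. At the On-therapy Visit, urine formed before the dose already contains drug from earlier doses.

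Optionally, Protocol Section 8.4 could state that the pool starts at a void just before dosing, whenever the bacteriology sample was taken.

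The SAP change costs a little extra summary work and needs no new data. The optional protocol change costs one sentence and, where the bacteriology void is not already close to dosing, one more void.
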